This study will be performed as a pragmatic controlled clinical trial. Patients fitting inclusion criteria who are admitted to the Vanderbilt University Adult Hospital will be enrolled in this study. Individual patient-level quasi-randomization will be employed. Odd-numbered MRNs will be assigned to the prone positioning and even-numbered MRNs will be assigned to the usual care arm. COVID-19 admissions will be reviewed during the daily COVID huddle, and appropriate study team personnel will facilitate protocol execution, working with the local providers/units.

5. Study Procedures

The study procedures in place involve treatment assignment, as well as electronic data capture. Day zero will be defined as the day of enrollment and treatment assignment. Data will originate from the electronic medical record for all patients, as well as from non-invasive patient wearable positioning sensors for a random subset to ensure protocol fidelity. Patients will be assigned to either one of the two comparator arms. Patients and providers will necessarily be unblinded, but outcomes will be analyzed by a blind assessor. Study arm assignment and the corresponding protocol will be discussed at the beginning of each day during the daily COVID-19 huddle. Workflow will include an initial run in period as we expect implementation uptake to take time. Patients enrolled during this ramp-up and optimization period will be allocated to

Study Protocol: Version 7.0 - October 29, 2020

Full Study Title: Pragmatic Trial Exploring Impact of Patient Positioning in the Management of Patients Infected with COVID19: Supine vs. Prone

Primary Investigator: [name], MSc

either the prone or usual care group as appropriate, but their data will not be included in the final analysis.

Comparator Arm A: COVID-positive patients who require supplemental oxygen, but are not yet mechanically ventilated, will be encouraged to lay in a completely prone position for as much time as is tolerable during hospitalization. Guidelines to ensure standardization include the following:

- Instructions to care-giving teams on how to frame the prone positioning ask to patients
- Request that clinical team provide reminders to the patient to prone if they are able (as feasible given workloads)
 - Suggest putting a pillow under pelvis/abdomen and under the lower legs to alleviate lower back strain
 - Suggest listening to podcast, music, or audiobook

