The scale remains ordinal in nature. We will use the approach of last value carried forward for patients who are not observed for the full five days. Patients discharged home will be at the bottom end of the scale (generally room air) while those who die will be scored the worst possible outcome. Patients discharged to long term care facility or similar will have their oxygen needs at transfer noted as their final requirements. We do not expect many patients to fall into this category since the endpoint is being measured relatively close in time to the intervention (5 days), and transfer is likely to occur after much later in the clinical course.

Study Protocol: Version 7.0 - October 29, 2020

Full Study Title: Pragmatic Trial Exploring Impact of Patient Positioning in the Management of Patients Infected with COVID19: Supine vs. Prone

Primary Investigator: [name], MSc

In the absence of any pre-existing information about our ordinal outcome, and rapidly evolving statistical capabilities to analyze these data being led by our group and others around the world, we describe a traditional analytical approach with associated sample size considerations. We recognize that in the coming weeks new methods will greatly improve the statistical efficiency of these trials and allow us to draw conclusions from fewer patients enrolled. Importantly, evolving approaches will be Bayesian in nature, which allows for early looks at the data so that we can understand the measurement properties of our ordinal scale and the impact of prone positioning and adjust as necessary.

We will use a proportional odds model to compare outcomes between study groups. Because it is possible that oxygen needs at day 5 are influenced by baseline oxygen requirements, we will adjust for baseline. This will answer the question: ‘for two patients who have the same oxygen requirements at baseline, will the patient who is in the prone positioning arm have lower oxygen requirements at day 5 than the person in the alternative arm’. Our final model will also adjust for age, BMI, smoking status, and baseline comorbidities.

Secondary analyses that involve continuous variables will generally use a proportional odds model with death always coded as ‘worst outcome plus one’. This will prevent bias associated with early death in COVID-19, which is known to have a high mortality right among hospitalized patients. For binary outcomes, a logistic model will be used.

Sample size considerations

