While data on the WHO ordinal scale are beginning to accrue, they are currently insufficient to understand the measurement properties for detailed sample size analyses. This is particularly the case because different institutions have different practices for use of supplemental oxygen, and given the novel nature of the disease it is not yet possible to protocolize this key outcome variable. In addition, we have modified the endpoint to be more granular and thus we expect it to provide greater power for discriminating differences between study groups. However, we are able to make some assumptions about the general distribution of the outcome scale based on the clinical course of patients admitted with oxygen at our institution, and we have powered our study according to that information. A general distribution across the seven-level ordinal scale at day five for patients with no intervention is as follows:

Death: 1%

Intubated: 5%

High flow nasal cannula (or CPAP, BiPAP): 14%

Supplemental oxygen: 30%

Hospitalized not on oxygen: 10%

At home with limitations/At home with no limitations: 40%

Our plan is to use a Bayesian approach. However, we have used a frequentist analysis to estimate the likely sample size under several assumptions about effect size. If we assume that

Study Protocol: Version 7.0 - October 29, 2020

Full Study Title: Pragmatic Trial Exploring Impact of Patient Positioning in the Management of Patients Infected with COVID19: Supine vs. Prone

Primary Investigator: [name], MSc

we reduce the need for oxygen and thus are able to discharge an additional 20% of participants by day 5, then 150 patients per group will have over 90% power to detect this difference. If we reduce the need for oxygen among a similar proportion of patients but only discharge an additional 10%, then 175 patients per group will have over 80% power to detect the difference. Given these estimates, we will plan to enroll 250 participants per study arm. When we have accrued 25 patients per arm, we will use the information to revise our sample size because we will then have enough information on which to base a Bayesian design.

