Following the interim analysis, the power calculation indicates that N=500 total will be needed to detect an OR of 1.6 with 80% power for the modified WHO ordinal scale at day 5. Due to concern over some missing data, potential crossover between arms, and to allow for measurements of body position sensors that are just now in use, an additional 10% of the sample size will be enrolled for a planned total of 550 patients enrolled at all sites.

9. Privacy/Confidentiality Issues

At no time during the course of this study, its analysis, or its publication will patient identities be revealed in any manner. The minimum necessary data containing patient or provider identities will be collected. As quickly as feasible, all data collected will be uploaded into a password-protected computerized database maintained within a secure, web-based application for building and managing online databases (REDCap), or stored on secure servers with user-level access control. All patients will be assigned a unique study number for use in the computerized database. At the time of publication all identifiers will be removed.

10. Follow-up and Record Retention

Given the adaptive nature of this trial, execution of this study will continue until a statistically significant result has been reached. Thus, we anticipate a study duration of no more than 12 months. For each participant, the study will commence at enrollment and study intervention will last until hospital discharge or in-hospital death. Patient clinical outcomes will be collected up until hospital discharge with final status for certain outcomes assessed with patient follow-up as needed depending on disposition. Identified data in the secure database will be stored for an indefinite period of time to allow for subsequent data analysis and future reference. However, all patients will be assigned a unique study number for use in the computerized database. At the time of publication, all identifiers will be removed.

References

1. Q&A on coronaviruses (COVID-19) [Internet]. [cited 2020 Mar 24]; Available from: <https://www.who.int/news-room/q-a-detail/q-a-coronaviruses>

Study Protocol: Version 7.0 - October 29, 2020

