The primary endpoint as an ordinal variable that quantifies provision of oxygen as the main measure of clinical status measured on the fifth day of enrollment. The basis of the outcome is the World Health Organization Ordinal Covid-19 Outcome Scale, and this has been combined with data concerning the intensity of oxygen requirements. Patients are first ranked by categories of oxygenation strategies from the least invasive to the most invasive. Then, within rank, they are assigned a score based on the oxygen delivery settings as follows:

- Death
- ECMO
- Mechanical ventilation (ranked by mean FIO₂ for the day)
- Non-invasive ventilation such as BIPAP (ranked by mean FIO₂ for the day)
- High flow nasal cannula (ranked by mean FIO₂ for the day, estimated from the %FIO₂ recorded on the device)
- Standard nasal cannula (ranked by mean FIO₂ for the day, FIO₂ on standard nasal cannula or face mask is estimated as $21 + 3 \times$ liters per minute (LPM) O₂ flow)
- Room air

To minimize missingness on this primary outcome, we use the approach of last value carried forward for patients who are not observed for the full five days. Patients discharged home are at the bottom end of the scale (generally room air) while those who die will be scored the worst possible outcome. Patients discharged to a long-term care facility or similar have their oxygen needs at transfer recorded as their final requirements. Not many patients are expected in this category because the endpoint is being measured relatively close in time to the intervention (5 days), and when transfers occur in this population, they are likely to occur after much later in the clinical course.

Secondary Endpoints:

The secondary endpoint is constructed the same way as the primary endpoint, but measured on each of the first five days of randomization.

Exploratory Endpoints:

A number of exploratory endpoints have been proposed for this trial, and additional outcome may be proposed as understanding of the underlying disease and treatment course evolves. Below, we list the pre specified exploratory outcomes. For newly proposed endpoints, the analytical approaches will generally be similar to those described below.

- Length of Stay
- ICU Length of Stay
- Intubation yes/no

- Ventilator-free days (VFDs) to 28 days, calculated as a backwards count of whole days from day 28 to the last day in receipt of mechanical ventilation.
- Oxygen Levels
 - Maximum FIO2 for each day 1-5 after enrollment

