- Maximum modified WHO ordinal scale score observed during 28 days of hospitalization, the modification is as follows:
 1. Death
 2. Hospitalized on invasive mechanical ventilation or ECMO
 3. Hospitalized on non-invasive ventilation or high flow nasal cannula
 4. Hospitalized on supplemental oxygenation
 5. Hospitalized not on supplemental oxygen
 6. Discharged/not-hospitalized (regardless of symptoms or organ support needs)
- Modified WHO COVID-19 ordinal scale measured at day 14

Safety endpoints:

- Incidence of Complications related to Positioning (e.g. accidental line displacement, vomiting, falls)

Datasets

Main Analysis

The main analysis for this study will be conducted using an intention-to-treat, or as assigned. All participants who met inclusion criteria and were randomized will be included. Participants will be grouped according to the arm to which they were allocated.

Safety Analysis

A safety analysis will be conducted to explore events associated with proning. This analysis will included all participants and events related to proning will be described regardless of study arm.

Other analyses

Neither a per protocol or complete case analysis is expected. A per protocol analyses might be justified if the number of major protocol deviations (including cross overs) exceeds about five in both arms combined.

Sensitivity analysis

This study was originally designed as a single-center pragmatic randomized controlled effectiveness trial. As the Covid-19 case waxed and waned across the country, and as demand for evidence for proning increased, the decision was made to open additional sites. One additional site was opened, which contributed less than 10% of participants to the dataset. We will repeat our main analyses excluded this additional site. If there are considerable differences, then we will report single site data.

Statistical Approach

Descriptive Analysis

Initially, we will describe the study cohort, both overall and grouped by intervention assignment. To characterize the study sample, demographic, clinical, and lab data will be described overall

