and by group. Groups will not be formally compared used statistical tests; differences and confidence intervals of differences may be reported. All categorical variables will be described using frequencies and proportions, and continuous variables will be described using mean, standard deviation, and percentiles (i.e. 25th , 50th , 75th). Missingness will be recorded for each variable. To further assess the distribution of variables, graphical summaries will be displayed using box-plots, dot-plots, violin-plots, and/or histograms. At a minimum, the following baseline variables will be described:

- Age (years)
- Sex (Male, Female, Not reported)
- BMI – kg/m²
 - Obesity (None, Stage I BMI 30.0 -34.9; Stage II BMI 35.0 – 39.9; Stage III BMI>=40.0, Not reported)
- Race (American Indian/Alaska Native, Asian, Black/African American, White, Other, Not reported)
- Ethnicity (Hispanic or Latino, Not Hispanic or Latino, Not reported)
 - Ethnicity may be combined with race
- Elixhauser Score
- Number of coexisting conditions (None; One; Two or more)
- Coexisting conditions (Yes/No)
 - Any
 - Diabetes
 - Hypertension
 - Underlying Respiratory Disease
 - Heart Disease
 - Renal Disease
 - Malignancies
- Smoking Status (as documented in the EMR)
- Renal replacement therapy required at enrollment (Yes/No)
- Vasopressors required at enrollment (Yes/No)
- Score on ordinal scale at enrollment (Hospitalized on low flow supplemental oxygen; Hospitalized on high flow supplemental oxygen; Hospitalized on non-invasive ventilation)

Subsequent to characterizing the cohort at baseline, we will explore and describe the outcome variables overall and grouped by study arm. We will take the same approach as for the cohort descriptors, using comprehensive summary statistics and graphical representations as appropriate. For depicting clinical course, alluvial or Sankey plots maybe be used.

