In the proportional odds model we assume that the relationship between each level in the outcome variable is proportional, so the effect that describes the relationship between the lowest category versus all higher categories of the outcome variable is the same as the relationship that describes the next lowest category and all higher categories. The proportionality assumptions will be explored graphically e.g. the logit of the empirical cumulative distribution function of the outcome should be parallel among categories of covariate X_j , and a partially proportional odds model may be pursued. The covariates that will be included in the model are those listed in the descriptive analyses, which include the important variable of baseline severity. Duplication of comorbidity variables will be avoided; only the Elixhauser score will be used. To check other model assumptions, the approaches described in Regression Modeling Strategies (Harrell 2015, 2nd ed.) will be used, i.e. we will assess the model fits, residual plots, partial effect plots, and/or anova plots (Wald minus the d.f.) will be displayed. Model results will be summarized with point estimates, 95% C.I., and p-values displayed in tabular form or graphically, along with model fit statistics.

Secondary Analysis

We have specified a single primary endpoint, and so we are not adjusting for multiplicity. Since our secondary endpoint should be more sensitive than the primary for changes in the outcomes, we are not employing a gatekeeping strategy. We will proceed with the secondary analysis regardless. With up to 5 outcome measurements per patient, a proportional odds model will be specified to include the random effect of patient and we will include number of days since enrollment. We will additionally include the time by treatment interaction to determine whether there is a differential treatment effect of proning over the observational window.

For exploratory outcomes, binary outcomes will be modeled assuming a logit link function, and ordinal and discrete outcomes will be modeled using a proportional odds model. Similar approaches will be used to modeling as for the main analyses.

Missingness

We do not expect missingness on our primary outcome. There may be missingness on covariates or on secondary or exploratory outcomes. We will not exclude cases with missing covariates. We will use multiple imputation with predicted mean matching. Cases with missing outcomes may also have the outcomes imputed

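### The primary model has no term for enrolment date or site; adding both is a cheap gain in precision and a guard should the arm mix drift under predictable allocation

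*SAP*

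**What the plan says.** The SAP (Main Analysis) defines the covariates of the primary model by pointing to the descriptive list: "The covariates that will be included in the model are those listed in the descriptive analyses, which include the important variable of baseline severity". Comorbidity is reduced to the Elixhauser score. The list, introduced with "At a minimum, the following baseline variables will be described", covers age, sex, BMI, race, ethnicity, comorbidity, smoking, renal replacement therapy, vasopressors and the ordinal score at enrolment. The protocol (section 8) adjusts for baseline oxygen need and adds: "Our final model will also adjust for age, BMI, smoking status, and baseline comorbidities". Neither list has enrolment date or site. The days-since-enrolment term in the SAP's secondary model is follow-up time, not calendar time.

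On allocation, the protocol (section 4) says: "Odd-numbered MRNs will be assigned to the prone positioning and even-numbered MRNs will be assigned to the usual care arm". Section 5 says that patients and providers are unblinded.

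On setting, the protocol's sample size section notes that "different institutions have different practices for use of supplemental oxygen, and given the novel nature of the disease it is not yet possible to protocolize" the outcome variable. Section 10 says "we anticipate a study duration of no more than 12 months". The SAP (Sensitivity analysis) explains why the trial went beyond a single centre: "As the Covid-19 case waxed and waned across the country, and as demand for evidence for proning increased, the decision was made to open additional" centres. In the event only one was added, and it gave under 10% of participants. The main analyses are to be repeated without it, and single-site results reported if the difference is considerable.

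**The concern.** The endpoint measures a care decision as well as a disease state. By the plan's own account that decision varies by institution and could not be standardised, so site plausibly predicts the outcome. Over up to a year of a new disease, calendar time plausibly does too.

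Two things are at stake. The first is efficiency: a prognostic variable left out of a proportional odds model costs some precision and pulls the conditional OR slightly towards 1. The second is protection. The arm is fixed by a digit that can be read before the patient is enrolled, and staff are unblinded. If willingness to enrol odd- and even-numbered patients changed differently over the study, the arm share would move with calendar time, and any time trend in the outcome would enter the treatment OR. As written, the plan would neither adjust for this nor display it. The SAP's interaction tests cover baseline characteristics only, so a treatment contrast that faded over the year would not be looked at either.

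**Working it through.** **Inputs from the documents.** N=500 for OR 1.6 at 80% power, raised to 550. Day-5 control distribution: 40% at home, 10% in hospital without oxygen, 30% on oxygen, 14% on high flow or non-invasive support, 5% intubated, 1% dead.

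**Assumptions.** Two-sided alpha of 0.05 (not stated, but consistent with the planned 95% intervals). The documents give no time or site effect, so these are ranges: an OR of 2–4 from start to end of enrolment, linear on the log scale, and a site OR of up to 2. In the planned model these stand for what remains after the listed covariates.

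**1. The plan's figure.** Whitehead's formula is N = 12(z_a + z_b)² / [(ln OR)²(1 − Σp̄³)], with p̄ the category share averaged over arms. Here (1.960 + 0.842)² = 7.85, (ln 1.6)² = 0.2209 and 1 − Σp̄³ = 0.880. So N = 12 × 7.85 / (0.2209 × 0.880) ≈ 485, and power at 500 is 0.81. This agrees with the stated 500. At N=550 the SE of the log OR is √(12 / (550 × 0.880)) ≈ 0.157.

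**2. Arm share constant at 1:1.**
- *Null.* In simulated samples of 300,000 with time OR 2–4 and site OR 1–2, the fitted OR without the terms was 0.998–1.003. There is no bias.
- *True OR 1.6.* Without the terms the fitted OR was 1.58 (time OR 2), 1.57 (time OR 4) and 1.56 (time OR 4, site OR 2). With them it was 1.59–1.60.
- *Precision.* A linear trend adds latent variance (ln OR)²/12, against 3.29 for the logistic error. For OR 2 this is 0.040/3.29 ≈ 1.2%; for OR 3 it is 0.101/3.29 ≈ 3.1%.
- *Power.* At N=500 and time OR 4 it was 0.77 without the terms and 0.79 with them (400 runs), which is within simulation error.

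**3. Arm share drifting with time.** Let t be uniform on 0–1 and P(prone | t) = 0.5 + d(t − 0.5). The arms then differ in mean t by d/3, so the log OR shifts by ln(trend OR) × d/3.

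| Prone share | Trend OR | Shift in log OR | Null OR becomes | Two-sided false positives |
|---|---|---|---|---|
| 40% to 60% (d=0.2) | 2 | 0.046 | 1.05 | 6.0% |
| 40% to 60% | 3 | 0.073 | 1.08 | 7.5% |
| 30% to 70% (d=0.4) | 2 | 0.092 | 1.10 | 9.1% |
| 30% to 70% | 3 | 0.146 | 1.16 | 15.4% |

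The last column uses SE 0.157. A drift in the opposite direction gives the reciprocal ORs. Large simulated samples with trend OR 2–4 gave 1.05–1.09 for the smaller drift and 1.10–1.19 for the larger. With date and site in the model they gave 0.99–1.01.

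**4. How far chance alone would move the share.** With N=550 enrolled uniformly, the SE of d is √(0.25 × 12 / 550) = √(3/550) = 0.074. So d=0.2 is 2.7 SE and d=0.4 is 5.4 SE. Drifts of this size would have to be systematic.

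**5. Site alone.** With 9% of patients at the second site, site OR 2 and a prone share there of 40% or 30%, the null OR is 0.98 or 0.96. With the term it is 1.00.

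**The case against.** The strongest reply is that concurrent allocation already does the work. Parity gives an expected 1:1 ratio at every date and site, so changing patients or changing practice affects both arms alike. That stands. A reader might infer that any drift in who is enrolled biases the OR; it does not. Chance imbalance over time is already covered by the nominal 5%, and nothing in the documents shows that the arm share moved.

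A second reply is that site is dealt with. This stands in part: the added site is small and the main analyses are repeated without it. But that analysis leaves calendar time untouched, and no threshold is given for a considerable difference.

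Third, the setting should not be overstated. A reader might take the SAP to say that treatment changed during the trial. Its words are that "additional outcome may be proposed as understanding of the underlying disease and treatment course evolves", offered as a reason for new exploratory outcomes. The remark on cases rising and falling explains why sites were opened; it does not describe this trial's enrolment. The protocol also drops run-in patients from the final analysis, which would remove the earliest uptake period, though the SAP does not repeat that exclusion.

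Fourth, the descriptive list is a minimum, so date and site could be added later. They could, but covariates added once results are known would look post hoc.

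**Conclusion.** The omission is real: neither term is in the primary model, and calendar time is handled nowhere. Its consequence is modest. With a constant arm share there is no bias at the null, a loss of about 1–3% in effective sample size (assumed trend OR 2–3), and attenuation of a true OR of 1.6 to about 1.56–1.58 (assumed time OR 2–4, with site OR 2 at the low end).

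Bias is conditional on the arm share also changing with time or site. The documents make that possible, through a knowable allocation digit and unblinded care, but give no evidence of it. On the assumed 40% to 60% drift with a residual trend OR of 2–3, a null OR would become about 1.05–1.08. The larger figures in the table need a drift that nothing in the documents suggests. They should not be read as the trial's expected error rate.

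This is a cheap improvement to the SAP, not a flaw that invalidates the planned comparison.

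**What to change.** Amend the SAP, before outcomes are seen by arm:

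- Main Analysis: add enrolment date (restricted cubic spline, three knots) and a site indicator to the covariates.
- Sensitivity analysis: keep the planned repeat without the second site.
- Descriptive Analysis: report enrolment by arm over calendar time, so that any drift in the arm share is visible.
- Exploratory: from a separate fit with a treatment-by-date interaction, plot the treatment OR over enrolment date.

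The cost is SAP wording and 3–4 model degrees of freedom among 550 patients: two for the spline and one for site, or four in all with an extra knot. Enrolment date and site are already recorded. One limit should be stated alongside: adjusting for date does not remove selection that differs by arm within the same period.

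### If day is linear and daily scores are serially dependent, the secondary model's patient random effect alone understates the standard error of the time-by-treatment interaction

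*SAP*

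**What the plan says.** The SAP (Secondary Endpoints) defines the endpoint thus: "The secondary endpoint is constructed the same way as the primary endpoint, but measured on each of the first five days of randomization". The model is in the SAP under Secondary Analysis: "With up to 5 outcome measurements per patient, a proportional odds model will be specified to include the random effect of patient". On time it says only that "we will include number of days since enrollment", without saying whether day is numeric or categorical. The interaction has a stated purpose: "We will additionally include the time by treatment interaction to determine whether there is a differential treatment effect of proning", over the observation window. The same section says "we are not employing a gatekeeping strategy" and makes no multiplicity adjustment.

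Neither document names a serial-correlation term, a previous-state term, a random slope, or a robust or bootstrap variance for this model. The reporting rule stands under Main Analysis: "Model results will be summarized with point estimates, 95% C.I., and p-values displayed in tabular form or graphically". A two-sided 5% level is implied by those intervals; it is not stated for this test.

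On patients not observed for all five days, the SAP (Primary Endpoint) says "To minimize missingness on this primary outcome, we use the approach of last value carried forward". That sentence concerns the primary outcome. Whether it reaches the daily secondary scores has to be inferred.

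**The concern.** A random intercept treats days 1 and 5 as being as alike as days 1 and 2. Oxygen support on consecutive days is likely to be more alike than support several days apart, and death, once scored, persists. A linear time slope contrasts late days with early ones, so its variance depends on how correlation decays with lag. If the true correlation decays and the model assumes it does not, the slope, and the arm difference in slopes, is reported with too much precision.

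At stake is the finding this term is meant to deliver: that proning works differently early and late in the five days. Such a finding would be false more often than its p-value suggests.

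**Working it through.** **The plan's own figure.** The documents give no figure for the secondary model. The nearest is the primary power: 80% at N=500 and an odds ratio of 1.6 (Protocol, Sample size considerations). With the day-5 distribution listed there (1/5/14/30/10/40%), let p̄ be the category proportions averaged over the two arms. The proportional odds information is V = (N/12)(1 - Σp̄³) = (500/12)(0.8804) = 36.68. Then ln(1.6)·√V = 0.470 × 6.057 = 2.847, and power = Φ(2.847 - 1.96) = 81.2%. The stated figure reproduces within 2 points, so that distribution is a reasonable base for simulation.

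**Closed form (Gaussian analogue).**
- From the SAP: five daily scores, a patient random effect, a day term and a day-by-arm term.
- Assumed: linear day, AR(1) correlation r, a share n of within-patient variance that is independent daily noise, and two-sided 5%.
- True correlation: S = (1-n)·AR(1) + n·I. Fitted exchangeable matrix M: same variance, same mean correlation m = (1-n)(4r + 3r² + 2r³ + r⁴)/10.
- Slope contrast c = (-2, -1, 0, 1, 2). c'Sc = 10 + 2(1-n)(4r - r² - 4r³ - 4r⁴) and c'Mc = 10(1-m).
- False-positive rate = 2[1 - Φ(1.96/√ratio)], with ratio = c'Sc/c'Mc.

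Example, r = 0.6 and n = 0: m = 0.404; c'Mc = 5.958; c'Sc = 10 + 2(0.6576) = 11.315; ratio 1.90; √ratio 1.378; rate 15.5%.

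| Noise share n | r = 0.2 | 0.3 | 0.6 | 0.9 |
|---|---|---|---|---|
| 0 | 8.1% | 9.9% | 15.5% | 20.8% |
| 0.2 | 7.4% | 8.8% | 12.5% | 12.2% |
| 0.5 | 6.5% | 7.2% | 9.0% | 7.6% |

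At n = 0.7 the range over these r is 5.9-7.2%, and at n = 0.8 it is 5.6-6.4%. A genuine patient intercept does not alter the rates, because it cancels from a contrast that sums to zero. For the five-day average the variance ratio is 1.00 throughout, since M is matched on mean correlation. With categorical day (4-df joint test) the rates are 5.2-7.9% at n = 0 and 5.1-5.9% at n = 0.2 to 0.5.

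**Ordinal simulation under the null.** N=500; five levels standing in for ranking by FIO₂ within device; the Protocol's day-5 distribution (50% room air or home, 30/14/5/1% above that); absorbing death; random-intercept proportional odds model; Wald test. Assumed: baseline device split 70/20/10 and a latent trend of 0.2 SD per day. The carry-forward variant was calibrated so that 40% are home at day 5, from the Protocol's "At home with limitations/At home with no limitations: 40" per cent. False-positive rates with linear day, at r = 0.3 / 0.6 / 0.9:

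| Noise share | No carry-forward | Carry-forward |
|---|---|---|
| 0 | 10.5 / 13.0 / 17.0% | 13.3 / 15.7 / 17.0% |
| 0.2 | 8.2 / 11.4 / 10.0% | 10.1 / 16.5 / 13.7% |
| 0.5 | 7.6 / 7.2 / 6.8% | 10.7 / 10.9 / 8.4% |

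The no-noise, no-carry-forward cell comes from a separate run. The others used 500 trials per setting (Monte Carlo SE 0.8-1.7 points). In those runs:
- categorical day gave 3.4-7.2%, rising to about 10-11% only with heavier carry-forward than the Protocol's distribution implies;
- a patient-clustered sandwich on the linear-day fits gave 2.6-6.0%.

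The exchangeable control gave 4.5%.

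A separately coded simulation without daily noise agrees: 9.2-16.6% for r = 0.3 to 0.9 without carry-forward (its correctly specified control gave 6.2%), and 10.6-18.0% across all its settings with carry-forward and absorbing death. The 10.6% arose where the underlying process was a pure random intercept.

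**The case against.** The strongest reply is that three conditions are needed and the documents fix none of them: day entered linearly, the patient effect meaning an intercept only, and serial dependence beyond it. This stands, and the point is conditional for that reason. An intercept is the natural reading of an unqualified patient effect, and a number of days reads most naturally as numeric, but neither is certain. With categorical day there is little left to correct.

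A reader might infer that the false-positive rate is 6.5-21%. The documents do not support that range. The top is the Gaussian approximation at r = 0.9 with no daily noise. The bottom is only where the noise share stops at 50%, and at 80% it falls to 5.6%. The simulated 7.6, 7.2 and 6.8% have exact 95% intervals of about 5.4-10.3, 5.1-9.8 and 4.8-9.4%, so they show little beyond Monte Carlo error.

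A reader might also assume that carry-forward applies to the daily scores and take the higher rates. The text pulls both ways. Building the secondary endpoint like the primary suggests carry-forward. Allowing a maximum of five measurements, and foreseeing missing and possibly imputed secondary outcomes (SAP, Missingness), suggests otherwise.

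The SAP's general model checks are only a partial answer. They are set out under Main Analysis, which has one score per patient, and do not mention within-patient correlation. The absence of gatekeeping is a declared, separate choice and adds nothing to the standard-error argument.

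**Conclusion.** The point holds conditionally and is minor. With linear day and serial dependence, the model-based standard error of the time-by-treatment term is too small. The illustrative false-positive rate runs from barely above 5%, when independent noise dominates, to about 7-17% in the tabulated simulations; the separately coded one reached 18.0% with carry-forward. These rates rest on an assumed daily correlation, noise share and discharge pattern, and on a 5% level implied by the 95% intervals.

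It would be wrong to infer that the trial's main result is in doubt. The primary analysis uses one day-5 score per patient and is unaffected. The time-averaged secondary effect is not shown to be affected, and no decision or stopping rule hangs on the interaction.

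**What to change.** Keep the same proportional odds model and estimand. Specify that the confidence interval and p-value for the time-by-treatment interaction come from a patient-clustered sandwich variance, or from a bootstrap that resamples whole patients. State alongside whether day is linear or categorical, and whether carry-forward applies to the daily scores.

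A model conditioning on the previous day's state estimates a different effect, on the next-day transition. It belongs only in a sensitivity analysis labelled as such.

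The cost is SAP wording, a little computing and a somewhat wider interaction interval. Under serial dependence the clustered standard error was about 1.1 to 1.4 times the model-based one (1.09-1.43 in the 500-trial settings, 1.20-1.46 in the run without noise or carry-forward). When the data were truly exchangeable it was 1.02 times, so little is lost if the random intercept proves adequate.
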